### **5. Gender of the Subjects**

**A. Are there any enrollment restrictions based on gender?**

No

**6. Age Range of Subjects**

**A. Will adults be enrolled ?**

Yes

**1. What is the age range of the adult subjects?**

19 years and older

**2. What is the rationale for selecting this age range?**

This study aims to explore smartphone app technology in the adult population. We have determined in our previous work with this population that the adults being served at this clinic location have an interest in using mobile apps.

**B. Will children (18 years of age or younger) be included in this research?**

No

**1. What is the justification for excluding children from participating in this research?**

Research is irrelevant to children (e.g. disease or condition rarely encountered in children). Knowledge being sought in the research is already available for children or will be obtained from another ongoing study.

♦ A separate study in children is warranted and preferable.

Insufficient data are available in adults to judge the potential risk in children.

Other. Explain.

**7. Race and Ethnicity**

**Are there any subject enrollment restrictions based upon race or ethnic origin?**

No

**8. Vulnerable Subjects**

**A. Will prisoners be included in the research?**

No

**B. Select from the list all of the vulnerable populations that will specifically be recruited to participate in this research.**

Decisionally-impaired persons

Critically ill patients

Students of the investigator

Employees of the investigator

- ◆ Educationally disadvantaged individuals
- ◆ Socially or economically disadvantaged individuals
- ◆ Individuals with a stigmatizing illness or condition
- ◆ Individuals from a marginalized social or ethnic group

Other.

No vulnerable subjects will be specifically recruited

**Describe the additional safeguards to protect the rights and welfare of the educationally disadvantaged individuals.**

1. An informed consent detailing the procedure and purpose of the study will be implemented. The researchers will ensure that participants understand that participation is completely voluntary with option of withdrawal at any time.
2. In an effort to protect the rights and welfare of educationally disadvantaged individuals delayed consent will be offered. In the event that the study personnel and/or the potential participant appears to need additional time to process the information necessary to make an informed decision additional time will be allotted to do so. The potential participant will also be encouraged to contact a family member or significant other to assist them in making an informed decision about whether or not to participate. The consent document will be reviewed with the participant, the study personnel will answer their questions, ensure their understanding of the study, give them a copy of the informed consent and ask them to think over their potential participation.
3. For semi-structured interviews, participants will be mailed a copy of the consent form one-week prior to their participation or handed the consent at their baseline surveys. They will be encouraged to review the consent form, prior to the interview meeting and discuss their participation with a member of their family or a friend. At the interview, the consent form will be read aloud and they will have an opportunity to individually ask questions with research personnel. Participants will also be assured that their participation (or not) will not impact their relationship with clinic staff.

**Describe the additional safeguards to protect the rights and welfare of the socially or economically disadvantaged individuals.**

1. An informed consent detailing the procedure and purpose of the study will be implemented. The researchers will ensure that participants understand that participation is completely voluntary with option of withdrawal at any time.
2. In an effort to protect the rights and welfare of socially or economically disadvantaged individuals delayed consent will be offered. In the event that the study personnel and/or the potential participant appears to need additional time to process the information necessary to make an informed decision additional time will be allotted to do so. The potential participant

will also be encouraged to contact a family member or significant other to assist them in making an informed decision about whether or not to participate. The consent document will be reviewed with the participant, the study personnel will answer their questions, ensure their understanding of the study, give them a copy of the informed consent and ask them to think over their potential participation.

**Describe the additional safeguards to protect the rights and welfare of the individuals with a stigmatizing illness or condition.**

1. Previously, when we conducted a focus group (approved by UNMC IRB), we explained to the patient participants ahead of time that the data will be collected in a group setting with individuals who have a diagnosis of depression. For this study, we will use the same approach, and highlight with the patients during the consent process that the study will be conducted in a group setting and be comprised of individuals who have diagnosis of a mental health condition to participate in the focus group.
2. The focus group will be conducted only by [name] and student research assistants so that other project team members will not know the identity of the patients.
3. For semi-structured interviews/focus groups participants will be mailed a copy of the consent form one-week prior to their participation or handed the consent at their baseline surveys. They will be encouraged to review the consent form, prior to the interview meeting and discuss their participation with a member of their family or a friend. At the interview, the consent form will be read aloud and they will have an opportunity to individually ask questions with research personnel. Participants will also be assured that their participation (or not) will not impact their relationship with clinic staff.
4. Prior to the start of the focus group/interview, all participants will be reminded the following of the inclusion criteria and the importance of protecting one another's privacy. Prior to the group starting the research team will instruct the participants that the members of the group and information that is shared within the group should not be shared outside the group to protect one another's privacy and confidentiality. We will reinforce the importance of not putting private information into the apps during mobile app exploration.
6. Any study related materials will be locked in the cabinet of the PI or stored in the password-protected project folder in the server, which can be only accessible by the team member.

**Describe the additional safeguards to protect the rights and welfare of the individuals from a marginalized social or ethnic group.**

1. An informed consent detailing the procedure and purpose of the study will be

implemented. The researchers will ensure that participants understand that participation is completely voluntary with option of withdrawal at any time.

2. In an effort to protect the rights and welfare of individuals from a marginalized social or ethnic group delayed consent will be offered. In the event that the study personnel and/or the potential participant appears to need additional time to process the information necessary to make an informed decision additional time will be allotted to do so. The potential participant will also be encouraged to contact a family member or significant other to assist them in making an informed decision about whether or not to participate. The consent document will be reviewed with the participant, the study personnel will answer their questions, ensure their understanding of the study, give them a copy of the informed consent and ask them to think over their potential participation.

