#### **Research Assessment for Patients**

- Trauma History Questionnaire
  - The Trauma History Questionnaire (THQ) is a 24-item self-report measure that examines experiences with potentially traumatic events such as crime,

general disaster, and sexual and physical assault using a yes/no format. For each event endorsed, respondents are asked to provide the frequency of the event as well as their age at the time of the event. The THQ can be used in both clinical and research settings, and is available in English. Will be assessed at Baseline

- Promis-Emotional Distress Depression Short Form 8a
  - is an 8 item self-report measure and this is not a diagnostic screening., Baseline and follow-ups
- Post-Traumatic Stress Disorder Checklist for DSM-5 (PCL-5): Baseline and two follow-up visits
  - 20 item report assesses for the 20 DSM-5 symptoms of PTSD.
- Pittsburgh Sleep Quality Index: Baseline and two follow-up visits
  - 19 questions rated by the participant and 5 by a bed partner (if available). Used to assess sleep quality and broken down into 7 components.
- mHealth App Usability Questionnaire (MAUQ): After the 2nd visit
  - A reliable and validated tool assessing the usability of mHealth apps. Will be used to evaluate BounceBack Now
- User Burden Scale: After the 2nd visit
  - Evaluates the difficulty of use and burden the app may place on participants.

Research Assessment for BHP

- Self-Management Support in Behavioral Health Organizational Assessment Tool (SMS): Baseline
  - Designed to assist behavioral health organizations in delivering self-management support to clients managing serious mental illness.

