**D. What provisions will be in place to protect the subject's privacy? Check all that apply.**

- ◆ Ensuring that only personnel listed on the IRB application Section I.3(A-E) are present during the consent process.
- ◆ Ensuring that the fewest number of individuals possible are aware of the subject's participation in the research.
- ◆ Ensuring that the research activities are performed in as private of a place as possible.

Other. Explain.

**E. Does this research involve data banking at UNMC, NM, UNO or CHMC, or by an outside organization (e.g. NCI Cooperative Group, pharmaceutical company) for future**

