**29. Process of Informed Consent**

**A. When will the prospective subject/parent(s)/guardian(s)/LAR be approached relative to their/the subject's actual participation in the study?**

**For Aim 1 participants will be recruited with 2 methods. For Aim 1, patients who are interested as identified through clinical trial registry will be contacted by a member of the research team to review participation in the study and determine eligibility criteria and if eligible will complete the informed consent process for the semi-structured focus groups.**

**For Aim 1 only the BHPs ([name] and [name]) who are listed on this IRB application with ethical access will identify any participants that may be interested in the study.**

**For Aim 2, Participants will be identified using two strategies 1.) BHPs at any of the study sites will identify participants who are interested in the study and 2.) Participants who meet the opt in criteria will be sent an email communication which provides brief summations of the study. BHP will advertise the opportunity to participant in the research study during their standard of care appointment. Any participant who wishes to participate and meets eligibility criteria, will complete the informed consent process with one of the study site research staff or if preferred by the patient, through the QR code/survey link for consent completion.**

**In either instance participants will then have time to ask questions. Participants, at this time, will decide whether they wish to participate or not. It is estimated that the provider reading the informed consent document, answering participants' questions, and assuring understanding of the study will take 5-10 minutes, but additional time will be used if needed for delayed consent or discussion with family/friends if the patient desires and/or the BHP or research investigator believes they need more time to decide.**

**Approved methods pertaining to UNMC E-Consents will be used in the instance that the participant is presenting virtually for participation.**

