**D. How much time will be allotted to the process of consent?**

The consent process is likely to take between 5-10 minutes. However, more time will be provided if needed. We will follow up with the BHP, Clinical Staff, Providers and Administration's manager to determine BHP, Clinical Staff, Providers and Administration interest and invite those interested in participating to complete the informed consent. BHPs at the participating clinic site will identify patients who meet the eligibility criteria and determine interest in participation.

**E. How will the process of consent be structured for subjects who are likely to be more vulnerable to coercion or undue influence?**

Informed consent will be completed in the office of the BHP or with UNMC research Team member on this IRB approved who is identified via clinical trial registry or during their standard of care appointment. Consent will be completed virtually or in written format for in person visits, as such, it will be read aloud to participants. Participants will have additional time, if needed, for delayed consent and encouraged to discuss their participation with family/friends. Only Citi trained and UNMC IRB approved members of this IRB application will be performing consent.

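### Consent safeguards prompt patients to involve a relative, partner or friend, and allow the interview consent form to be mailed, with no caution for trauma linked to someone close

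*Combined protocol and SAP*

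**What the plan says.** Section II, item 8 lists safeguards for four vulnerable groups. For three of them (educationally disadvantaged, socially or economically disadvantaged, and marginalized social or ethnic groups) the delayed-consent item contains the sentence: "The potential participant will also be encouraged to contact a family member or significant other to assist them in making an informed decision".

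For interviews (educationally disadvantaged group) and for interviews or focus groups (stigmatizing-condition group), a further item says "participants will be mailed a copy of the consent form one-week prior to their participation or handed the consent at their baseline surveys". It then encourages them to read the form and to "discuss their participation with a member of their family or a friend".

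The consent section treats the same step in two ways. Item 29.E, on people more vulnerable to coercion or undue influence, says: "Participants will have additional time, if needed, for delayed consent and encouraged to discuss their participation with family/friends". Item 29.A allows extra time for "discussion with family/friends if the patient desires", and/or where the provider or investigator thinks more time is needed.

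On privacy, item 15.D ticks this provision: "Ensuring that the fewest number of individuals possible are aware of the subject's participation in the research".

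On the population, item 9 makes a trauma-related disorder or symptoms an entry criterion for Aim 2. The Trauma History Questionnaire in item 12.B covers events such as crime, "general disaster, and sexual and physical assault using a yes/no format".

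**The concern.** Advising a patient to talk to family before joining a study is usually protective. Here the patients are recruited around trauma and one study instrument asks about assault, so the person at home may be part of the history. A prompt from study staff to involve a partner or relative, or a consent form arriving at a shared address or mailbox, could tell that person that the patient is in a trauma study. That in turn says something about the patient's condition.

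The plan already shows care on this front. It suggests completing the Aim 2 survey in private and holds interviews in a private place or by video. The same care is not extended to the consent conversation or to delivery of the form. What is at stake is participant protection; the estimates and analyses are not touched.

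**Working it through.** No formula applies, and the plan states no figure to reproduce. The check sets the relevant places side by side.

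1. **How often the encouragement appears.** The sentence on a family member or significant other appears three times in item 8. The sentence on a family member or friend appears twice in item 8. Item 29.E adds one more. That is 3 + 2 + 1 = 6 places where the prompt comes from the study side. Only item 29.A ties the discussion to the patient's own wish, and even there staff judgement is an alternative trigger.

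2. **Whom it covers.** Item 4.A gives 10 patients for Aim 1 and 15 for Aim 2, so at most 10 + 15 = 25. Item 12.B expects almost all of them to be African American or low-income, so the item 8 safeguards would reach most of the sample.

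3. **Whether it is limited to patients needing more time.** The three sentences on a family member or significant other follow directly on the delayed-consent text and can be read as limited in that way. The two interview items are not: they address interview or focus-group participants generally.

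4. **Whether trauma linked to someone close is foreseeable.** Trauma is an entry criterion for Aim 2 (item 9), and assault is within the questionnaire's scope (item 12.B). The plan's description of the questionnaire does not address who the perpetrator was. The possibility is therefore an inference from population and instrument; the documents do not count it.

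5. **How the form travels.** Item 8 gives two routes, mailing or hand-over at baseline. Item 29.B, for consent more generally, lets mail be electronic or postal, and item 15.B records postal addresses, so a home mailing is possible. Contact preferences are collected: phone, text or email for Aim 1, and email, text or phone for Aim 2 follow-up. Aim 2 patients invited to interview also give preferred contact details for scheduling. None of these is linked to delivery of the consent form, and none asks whether the route is private.

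6. **Whether a caution appears elsewhere.** Item 16 names breach of confidentiality only in general terms. The private-setting advice in item 12.B concerns completing the Aim 2 survey. No section available limits the encouragement to someone the patient trusts, or makes an exception.

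**The case against.** The strongest reply is that nothing here is inconsistent. The neighbouring provisions in item 15.D concern which personnel attend consent and where research activities take place, so the provision is most naturally a duty on the study team. A patient who talks to a relative makes a voluntary disclosure, and both statements can hold. A reader might infer an outright contradiction with item 15.D, or with the private-setting advice for the survey; the documents do not support that. What remains is tension: the team undertakes to keep awareness small while prompting patients to widen it.

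A reader might also infer that every consent form is posted to the home. That is not supported either. Mailing is one of two options, applies to interviews and focus groups, and need not be postal. Nor is the whole sample selected for trauma, since the Aim 1 criteria do not require it. Several passages allow a friend instead of a relative, no patient is directed to any particular person, and Aim 2 patients already have a behavioral health provider who knows them.

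These points narrow the concern but do not remove it. Voluntary disclosure can still be prompted by staff, and the documents never tell staff when not to prompt it. The consent pages are not in the text available, so this says nothing about what the form itself contains.

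**Conclusion.** The point holds as a gap in participant protection and a mismatch of wording. Items 8 and 29.E have patients encouraged to consult people close to them, item 29.A is softer, and no section shown deals with a patient whose trauma involves such a person or whose mail is not private.

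The conclusion rests on one assumption: that some Aim 2 patients have trauma linked to a partner or relative. The entry criterion and the questionnaire make this foreseeable, but the documents give no share. A reader might be tempted to turn an assumed share into a probability that at least one patient is harmed, or to argue that such patients will decline and be under-represented. The first has no basis in the documents and the second is conjecture; neither is claimed here.

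The scale is small, at most 25 patients, and the planned analyses are unaffected. The change is still worth making because the risk is foreseeable, the correction is a matter of wording, and the procedures are meant to shape a larger trial (Addendum B).

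**What to change.** - In item 8 (all five sentences) and item 29.E, replace the encouragement with a patient-led option in line with item 29.A. Suggested text: *patients may, if they wish, talk it over with someone they trust, and need not tell anyone.* Keep delayed consent, the extra time and access to a team member for questions.
- In the two interview items of item 8, either hand the consent form over at baseline or send it only by the contact route the patient has chosen and confirmed as private. The contact details already collected in item 12.B can carry this, with one added confirmation question.

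The cost is a consent-process wording change and one item on an existing form. The downside is slightly less prompting of family support for patients who would have gained from it; they remain free to seek it.

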## **9. Inclusion Criteria**

### **What are the specific inclusion criteria?**

Behavioral Health Providers, Clinical staff, providers and administration

- 19 years and older

For Patients: Aim 1

- 19 years and older
- Being referred to a behavioral health provider at the Fontanelle or Midtown Clinic or receiving care at Fontanelle or Midtown clinic and contacting the research team through clinical trials registry
- Own a smart phone

For Patients: Aim 2

- 19 years and older
- Being referred to a behavioral health provider at the Fontanelle, Midtown or Old Market Clinics or receiving care at Fontanelle, Midtown Or Old Market clinics and contacting the research team through clinical trials registry

For Aim 2: Bluestem clinic location recruitment will only take place for Aim 2. So inclusion criteria for Aim 2 will include:

Patient is 19 years of age or older

Being referred to a behavioral health provider at the Fontanelle, Midtown, Old Market or Bluestem Clinic

Presence of Trauma Related Disorder or Trauma Related Symptoms as identified by BHPs or member of the research team.

## **10. Exclusion Criteria**

### **What are the specific exclusion criteria?**

Behavioral Health Providers, Clinical staff, providers and administration :

- 18 years and younger

Patients:

- 18 years and younger
- Does not own a smart phone
- No presence of Trauma Related Disorder or Trauma Related Symptoms as identified by the BHP or research team for Aim 2
- High suicidality based on a clinical assessment by the behavioral health provider
- Having neurocognitive conditions either assessed by a primary care provider or diagnostic code for neurocognitive condition found in the patient note or E.H.R.

## **11. Pregnancy and Contraception Requirements**

### **A. Are women of child bearing potential (WOCBP) included in this research?**

Yes

#### **a. Are there any specific contraception requirements for subjects?**

No

#### **1. Provide justification for absence of contraception requirements**

- ◆ There are no interventions that are likely to be of risk to a fetus
- Investigational drug(s) is (are) not systemically absorbed
- Investigational drug(s) is (are) systemically absorbed, but there is no evidence from human studies, or from clinical experience, that there is risk to a fetus
- Other

